University of Nottingham

Gut Imaging for Function & Transit in Cystic Fibrosis Study 1

Study protocol 1 September 2018, NCT03566550

Brief Summary

Many people with Cystic Fibrosis (CF) are troubled by symptoms from their stomach and bowels: their gastrointestinal (GI) tract. Symptoms affect quality of life and can also reduce people's ability to digest enough calories to remain healthy, leaving them undernourished and less able to deal with other health problems such as infection.

Clinical tests to assess bowel function are limited. Many tests involve inserting a sensor or camera into the bowel, so they are not suitable for long periods, and can be uncomfortable. In Nottingham the investigators have developed imaging scans which can assess how someone's digestion works without any invasive device. The type of scanning the investigators use is called Magnetic Resonance Imaging, or MRI.

The purpose of this study is to see if those scanning methods can be used in people with CF to understand their digestion and any problems they have.

Detailed Description:

This is a small pilot study to establish that differences in digestion between people with and without CF can be quantified by repeated MR scans in fasted participants in response to standardised meals.

Participants will complete questionnaires on gastrointestinal function and symptoms: the PAC-SYM questionnaire, validated to assess symptom burden in adults with chronic constipation; and the CF abdomen questionnaire, developed in German for use in young people and adults with cystic fibrosis.

After this, participants only need to attend one study day at the Sir Peter Mansfield Imaging Centre. On this day they will be asked to withhold any medicines specifically targeted to alter bowel habit. This shall include laxatives but not enzyme

replacement therapy. They should attend on the study day having fasted since waking, other than water for essential medicines.

They will have their first MRI scan fasted. After the scan they will eat a standard test meal, and be scanned again first at half hour, then hour intervals until six hours after the first meal. The final scan will constitute the end of the study for each participant. Each session in the MRI scanner will last around 15 minutes. After each scan they will score their abdominal pain, bloating and flatulence symptoms on a Likert scale. In between scans, participants will have access to a lounge with wi-fi and a television.

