Infection control requirements mean that the investigators are unable to scan more than one patient with CF on a single day. Patient scans will alternate with those of a Control participant. The investigators will aim to frequency match Controls with Patients for age and gender.

Study Design

Study Type: Observational

Actual Enrollment: 24 participants

Observational Model: Case-Control

Time Perspective: Cross-Sectional

Official Title: A Case-Control, Observational Study of the Postprandial Changes in Magnetic Resonance Imaging Parameters of Gastrointestinal Function and Transit in People With Cystic Fibrosis

Actual Study Start Date: September 4, 2018

Actual Primary Completion Date: February 20, 2019

Actual Study Completion Date: February 20, 2019

Group/Cohort	Intervention/treatment
CF people with cystic fibrosis	Diagnostic Test: MRI scans Repeated MRI scans imaging digestion of standard meals
Control people without cystic fibrosis	Diagnostic Test: MRI scans Repeated MRI scans imaging digestion of standard meals

Outcome Measures

Primary Outcome Measures:

1. orocaecal transit time [Time Frame: 1 day of scanning] - time taken after eating for ingested food to be identifiable in the caecum on MRI

Secondary Outcome Measures:

1. gastric volume [Time Frame: 1 day of scanning] - volume of stomach at each time point of digestion to measure speed of gastric emptying
2. small bowel water content (corrected for body surface area) [Time Frame: 1 day of scanning] - volume of water content in small bowel representing secretions
3. colonic volume (corrected for body surface area) [Time Frame: 1 day of scanning] - volume of colon representing ease of chyme passage through colon

4. gastrointestinal symptoms [Time Frame: 1 day of scanning] - gastrointestinal symptoms as measured by questionnaires to monitor relationship with outcomes measured by MRI

Other Outcome Measures:

1. T1 relaxation time of ascending colon chyme [Time Frame: 1 day of scanning] - An approximate measure of water content in chyme present in the ascending colon
2. Fat fraction of the ascending colon chyme [Time Frame: 1 day of scanning] - A measure of fat content in chyme present in the ascending colon

Eligibility Criteria

Ages Eligible for Study: 12 Years to 40 Years (Child, Adult)

Sexes Eligible for Study: All

Accepts Healthy Volunteers: Yes

Sampling Method: Non-Probability Sample

Study Population

Nottingham and surrounding towns

Inclusion Criteria:

- Age 12 - 40 years

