- Capacity to consent, or to understand the requirements of the study where parental consent is needed

PATIENTS: confirmed diagnosis of Cystic Fibrosis, either by sweat test or genetic testing; to reduce heterogeneity, we will only enrol homozygous CF patients with the most common CFTR mutation, p.Phe508del

CONTROLS: no clinical evidence or suspicion of Cystic Fibrosis

Exclusion Criteria:

Measurement of Forced Expiratory Volume in 1 second (FEV1) of <40% predicted using Global Lung Initiative criteria, according to clinical records

Contra-indication to MRI scanning, such as embedded metal, pacemaker

Unable to stop medications directly prescribed to alter bowel habit, such as laxatives or anti-diarrhoeals, on the study day

Previous resection of any part of the gastro-intestinal tract apart from appendicectomy or cholecystectomy. Surgical relief of distal intestinal obstruction syndrome or neonatal ileus will be permitted unless clinical records show excision of intestine >20cm in length.

Intestinal stoma

Diagnosis of inflammatory bowel disease or coeliac disease confirmed by biopsy

Gastrointestinal malignancy

Unable to comply with dietary restrictions required for the study

Statistical analysis plan

Data will be summarised through descriptive statistics. Differences between Patient and Control data will be tested using non-parametric methods. The software used will be GraphPad Prism version 7.0 or later, or SPSS version 21 or later, under licence to the University of Nottingham.

The primary and secondary outcomes will be compared firstly between CF patients and the non-CF controls using a t-test (for normally distributed variables) or a Mann-Whitney U test (for non-normally distributed data). We will then explore the association between the results of the symptom questionnaires and the MRI findings. We will compare MRI parameters such as OCTT, small bowel water and colonic volume against both the total CF Abdomen-Score and against the score for individual domains. An example of the latter would be comparing OCTT with the domains of “constipation” & “too much time spent on the toilet” from the CF Abdomen-score. We will compare these using a t-test or Mann Whitney U test, where the MRI parameter is a binary or categorical variable, and Pearson or Spearman’s correlation coefficient for continuous MRI parameters.

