Where data is missing, through participant withdrawal or technical failure (e.g. scanner breakdown), an imputed value will be assigned which will be the median value for that parameter of other participants in the participant group (Patient/Control) at that time point.

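### The median rule for missing data, as naturally read, replaces the primary outcome of an interrupted participant with the group-median OCTT and ignores the lower bound set by that participant's last negative scan

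*Combined protocol and SAP*

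**What the plan says.** The primary outcome, under Outcome Measures, is orocaecal transit time (OCTT): "time taken after eating for ingested food to be identifiable in the caecum on MRI". The Detailed Description sets the scans from which it is read. After a fasted scan and a test meal, participants will "be scanned again first at half hour, then hour intervals until six hours after the first meal".

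The last paragraph of the Statistical analysis plan gives one rule for missing data. It opens "Where data is missing, through participant withdrawal or technical failure (e.g. scanner breakdown" and continues "an imputed value will be assigned which will be the median value for that parameter of other participants in the participant group". The comparison set is "other participants in the participant group (Patient/Control) at that time point".

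No outcome is exempted. The same plan treats OCTT as one of the imaging parameters: "We will compare MRI parameters such as OCTT, small bowel water and colonic volume". The group comparison is made "using a t-test (for normally distributed variables) or a Mann-Whitney U test (for non-normally distributed data". The plan gives no method for censored times and no sensitivity analysis for the imputation.

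**The concern.** OCTT is an event time read from a series of scans. Each scan without food in the caecum shows that arrival comes later. A participant whose scanning stops early therefore has partial data: OCTT exceeds the time of the last negative scan. The median rule discards that information.

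Two things can follow. First, the entered OCTT may be a time at which the participant's own scan was negative. Second, a slow participant is recorded as typical. Only people without observed arrival need an imputed OCTT, and slower transit leaves more time in which to stop first, so the affected participants are likely to lean towards slow transit. If they are in the CF group and CF transit is slower, the group difference shrinks. If only one group loses its slow members and there is no true difference, a false one can appear. The same OCTT values also enter the planned comparisons with symptom scores.

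**Working it through.** **No figure to reproduce.** The documents give no power, alpha, effect size, SD or dropout rate. The contradiction follows from the text. Its size can only be illustrated.

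**1. Condition for a contradiction.** Let L be the last negative scan and M the median OCTT of the other group members. The images say OCTT > L and the rule enters M. The two conflict when M ≤ L.

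Example with assumed data: the 11 other members have OCTT 2, 2, 3, 3, 4, 4, 4, 5, 5, 6, 6 h. The sixth value is the median, so M = 4 h.

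| Last negative scan L | Entered under the median rule | Consistent with own scans? | Entered if arrival is imputed scan by scan |
|---|---|---|---|
| 3 h | 4 h | yes | 4 h (7 of 11 others arrived by then) |
| 4 h | 4 h | no | 5 h (9 of 11) |
| 5 h | 4 h | no | 6 h (11 of 11) |

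At L = 1 or 2 h there is no conflict either. Scan-by-scan imputation removes the conflict, but it still counts the person as arrived at the first missed scan by which most of the group has arrived.

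**2. Inputs for the simulations.** From the documents: "Actual Enrollment: 24 participants" and scanning to 6 h. Assumed: 12 per group (the split is not stated), lognormal OCTT with log-SD 0.35, scans at 30, 60, 90, 120, 180, 240, 300 and 360 min (the switch from half-hourly to hourly is not stated), OCTT read at the first scan at or after arrival, non-arrival by 6 h scored 420 min, and a two-sided 5% test.

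**3. How often the entered value conflicts with the scans.**

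| True group median | Last negative scan | Entered value at or before that scan |
|---|---|---|
| 210 min | 4 h | 85% |
| 210 min | 5 h | about 100% |
| 270 min | 5 h | 79% |
| 330 min | 5 h | 23% |
| 330 min | 4 h | about 1–5% |

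These rates are conditional on a late negative scan. In a separate simulation, one or two patients stopped at random scans (medians 3 v 4 h or 3.5 v 5 h, three readings of the schedule). There, 3% to 15% of imputed values conflicted, and power changed by about 2 points or less, not consistently downward.

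**4. Effect on the group comparison.** Two (three) members of one group stop after the 4 h scan and are imputed if still negative. Power is for medians of 330 v 210 min; false positives are for 210 v 210 min.

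| Who stops, and method | Power | False positives |
|---|---|---|
| Nobody; Mann-Whitney | about 81% | nominal 5% |
| Random members; median rule | about 2–3 points lower | 6–7% |
| Slowest members; median rule | 72% (67%) | about 15% (23%) |
| Slowest members; Gehan test, kept as later than 4 h | about 76% (72–74%) | about 5% |

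In the slowest-members case the mean difference falls from about 96 to 83 (74) min.

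**5. Reading the table.** A random leaver needs imputing only if still negative at 4 h. With median 210 min that probability is 1 − Φ(ln(240/210)/0.35) = 1 − Φ(0.38) ≈ 0.35, so two (three) leavers yield about 0.7 (1.05) imputed values. With median 330 min it is 1 − Φ(ln(240/330)/0.35) = 1 − Φ(−0.91) ≈ 0.82, or about 1.6 (2.5) values.

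The power loss at 330 v 210 min comes from the pull to the centre, not from contradicted scans. Forcing the entered value past the last negative scan left power the same (72.2% v 72.4% with two leavers, 66.1% v 66.6% with three).

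**The case against.** **The rule may not mean the group-median OCTT.** It refers to a value at a time point, which suits gastric volume or small bowel water. OCTT has no time point. If arrival were imputed at each missed scan, it could not precede the last negative one. This stands: a reader might infer that the plan necessarily enters values which the images exclude, and the text does not go that far. But the plan counts OCTT among the MRI parameters and exempts nothing, so the group-median reading is the natural one. The pull to the centre remains on either reading.

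**The large figures are a worst case.** A reader might infer a false-positive rate of 15% to 23% for this study. Nothing in the documents supports the loss of exactly the slowest two or three members of one group. Longer transit gives some tilt towards slow leavers, not that degree of selection. With random leavers the effect is small. This stands.

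**The figures depend on completers.** With median 330 min, 1 − Φ(ln(360/330)/0.35) = 1 − Φ(0.25) ≈ 40% have not arrived by 6 h, so the 420 min score affects power and the mean difference. This stands, and the score is therefore listed as an assumption. How completers without arrival are handled is a separate gap: they neither withdrew nor had a technical failure.

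**A missed scan followed by a positive one.** One might read the rule as overwriting such an OCTT. It need not apply, because an OCTT can still be read.

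**Exposure may be nil.** Participation is one scanning day in a small pilot, and no withdrawal or failure count is given. The rule may never have been used for OCTT. This limits the size of the concern but does not repair the rule.

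**Conclusion.** The point holds in a limited form. The plan does not say how its median rule applies to a single-valued event time. On the natural reading it discards a known lower bound on the primary outcome. The entered value contradicts the participant's scans whenever the last negative scan is at or after the other members' median; people who stop earlier than that are not contradicted. The pull of slow transit towards the centre does not depend on the reading.

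The real impact is unknown. Under the stated assumptions it is small for a few random leavers and material only if the slowest members of one group are lost. The documents do not support a claim that the primary comparison is in fact biased. With 24 participants and a cheap remedy, the rule should still be corrected.

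**What to change.** Exempt OCTT from the median rule and add a paragraph to the Statistical analysis plan:

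- If scanning stops before arrival through withdrawal or technical failure, record OCTT as later than the last negative scan.
- Compare groups with a censoring-aware rank test, Gehan-Wilcoxon or log-rank, chosen in advance.
- Keep OCTT as observed for anyone whose arrival was seen, including after a missed scan.
- Report, by group, how many OCTT values are affected.

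Recruitment and scanning are recorded as complete, so this can be applied at analysis or as a sensitivity analysis.

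The cost is one paragraph and no new data. The team should confirm that its named software runs the chosen test. OCTT would be summarised by a Kaplan-Meier median rather than a plain mean, and that median assumes that stopping is unrelated to later arrival. The change does not recover all the lost information: in the worst case above, Gehan power is still about 76% (72–74%), against about 81% with complete data.

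### Filling gaps with the participant's own group median and testing the result as observed data raises the false-positive rate of single-value comparisons: about 6% with one missing value, 7-8% with one per group

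*Combined protocol and SAP*

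**What the plan says.** The last paragraph of the Statistical analysis plan makes imputation the rule, not an option: "Where data is missing, through participant withdrawal or technical failure (e.g. scanner breakdown), an imputed value will be assigned". The value assigned is the one "which will be the median value for that parameter of other participants in the participant group (Patient/Control) at that time point".

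The paragraph before it compares Patients with Controls "using a t-test (for normally distributed variables) or a Mann-Whitney U test (for non-normally distributed data"). Neither paragraph adjusts the sample size or variance for imputed values, or provides multiple imputation or an analysis of observed values only. Read as written, an imputed value enters the test as if it had been measured.

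The outcomes are of two kinds. OCTT, under Primary Outcome Measures, is one number per participant: "time taken after eating for ingested food to be identifiable in the caecum on MRI". Gastric volume, under Secondary Outcome Measures, is a "volume of stomach at each time point of digestion to measure speed of gastric emptying". The SAP does not say whether such outcomes are tested scan by scan or as a summary over the day.

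**The concern.** A value placed at the centre of its own group carries no new information about the difference between groups. It nevertheless counts as one more participant and pulls the estimated spread down. Both effects make the standard error too small, even when the loss is pure chance.

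The Detailed Description says the pilot is to establish that "differences in digestion between people with and without CF can be quantified", and the Patient-Control tests are the first analysis planned. A rule that overstates the evidence for a difference bears directly on that aim. With about 12 per group, one lost participant is about 8% of a group (1/12).

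Withdrawal is one of the two causes the SAP names, and it removes every later scan. If outcomes are tested scan by scan, the same participant is imputed at each later time point and the error recurs in each of those tests.

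For OCTT, a rule tied to a time point does not fit an outcome with one value per person. If it is applied anyway, a participant who leaves with no caecal arrival yet seen could be given a transit time that their own scans rule out.

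**Working it through.** **Inputs.** Study Design gives 24 participants. No group sizes are stated; 12 v 12 is inferred from "Patient scans will alternate with those of a Control participant". The two-sided 5% level, the missing counts and missingness completely at random are assumptions. The plan gives no error rate or power figure to reproduce.

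**Closed-form check (t-test, normal data).** Replace the median by the mean of the observed values, which is nearly the same for symmetric data and allows exact algebra. Let n1 and n2 be the numbers observed, SS the within-group sum of squares and D the mean difference. Imputing at the mean leaves D and SS unchanged.

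- Correct statistic: D / √[SS/(n1+n2−2) × (1/n1 + 1/n2)], on n1+n2−2 df.
- Statistic as planned: D / √[SS/22 × 2/12], referred to 22 df (critical value 2.074).
- Squared ratio, planned to correct: R² = [22/(n1+n2−2)] × (1/n1 + 1/n2) / (2/12).
- True error rate: P(|t| > 2.074/R) on n1+n2−2 df.

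| Missing | R² | 2.074/R | df | Error rate |
|---|---|---|---|---|
| 1 in one group | 23/21 = 1.095 | 1.982 | 21 | 6.1% |
| 2 in one group | 1.210 | 1.885 | 20 | 7.4% |
| 1 per group | 264/220 = 1.200 | 1.893 | 20 | 7.3% |
| 2 per group | 264/180 = 1.467 | 1.712 | 18 | 10.4% |

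**Simulation with the median itself.** Null data, 200,000 replicates, normal values. The Mann-Whitney range runs from with to without the continuity correction.

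| Missing | t-test | Mann-Whitney |
|---|---|---|
| 1 in one group | 6.0% | 5.7-6.5% |
| 2 in one group | 7.4% | 7.5-8.5% |
| 1 per group | 7.2% | 7.3-8.3% |
| 2 per group | 10.6% | 11.9-13.1% |
| Observed values only, same patterns | 4.9-5.0% | 4.2-5.3% |

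A separate simulation agreed to within about 0.2 percentage points. Its Mann-Whitney figures were almost the same for lognormal, exponential and uniform data.

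**Where the effect is smaller.**

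- *t-test on skewed data* (one in one group, one per group, two per group): 5.5%, 6.5%, 9.6% for lognormal data with log-SD 0.5; 4.2%, 4.9%, 7.0% with log-SD 1. The t-test on observed values starts below 5% here (4.5-4.7% and 3.4-3.5%).
- *Average over the day.* The schedule is a fasted scan, then "be scanned again first at half hour, then hour intervals until six hours after the first meal". Read as 0.5, 1, 2, 3, 4, 5 and 6 h, that makes 8 scans. If the last 3 are lost by one participant the rate is 5.2-5.6%; by one per group, 5.7-6.0%; by two per group, 6.5-6.8%.

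**OCTT, only if the rule is applied to it.** Assume lognormal transit times with log-SD 0.4, read on the scan grid above. Take a participant who withdraws after the 4 h scan with no arrival seen. The imputed value is at or before 4 h in 97%, 50% and 7% of samples for group medians of 3, 4 and 5 h. Those shares apply only to participants with no arrival by 4 h, a state with probability 24%, 50% and 71%. Over everyone withdrawing then, the contradiction arises in about 0.97 × 0.24 = 23%, 0.50 × 0.50 = 25% and 0.07 × 0.71 = 5%. After the 2 h scan, the conditional share is 0.4% or less.

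**The case against.** The strongest reply is that little may be missing. Participants attend for one scanning day and the last scan ends their participation, so there are no follow-up visits to lose. If missing counts are drawn at random, the overall t-test error is 5.3% at 1% missing per value, 5.6% at 2%, 6.5% at 5% and 8.2% at 10%. At 5% missing, the chance of two or more losses in both groups is 1.4%: for one group 1 − 0.95¹² − 12 × 0.05 × 0.95¹¹ = 0.118, and 0.118² = 0.014. This stands as a limit on size, and it is why the two-per-group figures are a less likely case. These missing rates are assumptions too, and the rule operates only when something is missing.

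A second reply is that this is a small pilot with no stated alpha, power or confirmatory claim. That lowers the stakes but does not excuse the rule: the plan specifies tests, and analysing observed values is no harder.

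Stronger readings are tempting, and the documents do not support them:

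- *That the primary analysis is invalid.* The wording does not clearly reach OCTT, so what can be shown is an ambiguity with a conditional consequence.
- *That every outcome is affected.* The SAP does not say that scan-level outcomes are tested one time point at a time, and day averages with few missed scans barely move.
- *That symptom correlations are inflated.* The direction depends on whether the groups are pooled, which the SAP does not state. In pooled simulations with two imputed per group, the mean correlation fell from 0.592 to 0.533 in one setting and rose from 0.514 to 0.535 in another.

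**Conclusion.** The concern holds for comparisons that use one value per participant: a test at a single time point, or OCTT if the rule is applied to it. Closed form and simulation agree, and leaving the imputed values out returns the t-test to about 5%, so the imputation is the cause.

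The mechanism is certain. Its practical size is conditional on the assumptions listed above and on how many values are lost, about which the documents say nothing. A reader might infer that this study's tests run at 10-13%; that would need two losses in each group, which nothing in the documents indicates. The OCTT contradiction is possible, but its frequency rests wholly on assumed transit times.

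The rule should be changed: it gives a wrong error rate whenever it operates on such a test, and the correction is cheap.

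**What to change.** Rewrite the missing-data paragraph of the SAP:

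1. Make observed values the primary analysis, using the t-test or Mann-Whitney test already planned at each time point on the participants measured there.
2. Keep median imputation at most as a labelled sensitivity analysis.
3. State that the rule does not apply to OCTT. Treat withdrawal before arrival as censored at the last scan, and compare groups with a rank-based test that allows censoring, such as the log-rank test. In simulation with withdrawals censored at 2 h, its error was 5.0-5.5% (5.1-5.8% with nothing missing).
4. Report missing counts by group, time point and cause.

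Observed-only tests correct the variance error, not bias from withdrawal linked to earlier values. A repeated-measures model is an optional sensitivity analysis for that case, and only if it lets the variance differ between scans. A plain random-intercept model should not be used for per-scan tests: when the SD halves over the day, its per-scan error runs from 0.2% to about 12%. Nor should each participant's available scans simply be averaged, which is biased after early withdrawal if values change over the day.

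**Cost.** A short rewrite, one censored-data test not now in the SAP, and unequal n across time points. Interval width is proportional to t × √(2/n). Against complete data, one missing per group gives (2.086 × √(2/11)) / (2.074 × √(2/12)) = 1.05, about 5% wider. Two per group gives (2.101 × √(2/10)) / (2.074 × √(2/12)) = 1.11, about 11% wider. At an assumed difference of 1.2 SD, t-test power falls from 80% to 76% and 72%. That is the real cost of the lost data, which median imputation conceals.

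### A single missed scan is filled with other participants' median, ignoring the participant's own scans on either side; the loss is mainly accuracy of that one value and curve

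*Combined protocol and SAP*

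**What the plan says.** The closing paragraph of the Statistical analysis plan has one rule for all missing data: "Where data is missing, through participant withdrawal or technical failure (e.g. scanner breakdown), an imputed value will be assigned". The value assigned is the median, for the parameter concerned, of "other participants in the participant group (Patient/Control) at that time point". The rule works scan by scan and names scanner breakdown, which can be temporary. It therefore covers one missed scan followed by further scans as well as a participant who leaves for good.

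Under Detailed Description, participants are scanned fasted, eat a test meal, and then "be scanned again first at half hour, then hour intervals until six hours after the first meal". Every scan except the first and the last thus has one of the participant's own scans on each side.

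Three of the Secondary Outcome Measures are MRI volumes followed over this schedule. Gastric volume is defined as "volume of stomach at each time point of digestion to measure speed of gastric emptying"; the others are small bowel water content and colonic volume, both corrected for body surface area. The Statistical analysis plan also relates these measurements to symptoms person by person: "We will compare MRI parameters such as OCTT, small bowel water and colonic volume against both the total CF Abdomen-Score".

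Nowhere do the documents separate an intermittent gap from dropout, use the participant's own scans to fill a gap, or plan a sensitivity analysis for the fill.

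**The concern.** When a participant leaves for good, there are no later scans to draw on. When one scan is lost and the next goes ahead, the participant's own values, 30 to 60 minutes either side on the hour and half-hour schedule, are to hand, and the rule ignores them. Someone whose colonic volume is consistently large is moved to the middle of the group for one scan and then returns, so the curve shows a drop and rebound that did not happen.

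What is at stake is the accuracy of individual serial values in a pilot whose stated purpose is to show that differences in digestion can be quantified by repeated scanning. The remedy needs only data that are already collected.

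**Working it through.** The documents give no SD, correlation, missingness rate or related figure, so there is no stated number to reproduce. The size below is an illustration.

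**Inputs**
- Total enrolment 24 (Study Design). The split by group is not stated; 12 per group is assumed, so a median is taken over 11 others.
- One interior scan missing in one participant.
- Values expressed as deviations from the group curve, in between-person SDs, with the same SD at each scan (assumed).
- Correlation ρ between any two scans of the same person, equal for all pairs (assumed; range shown).

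**Error of the planned fill.** The missing value and the others' median are independent, so the error variance is 1 + v, where v is the sampling variance of a median of 11. By simulation v = 0.137. The RMS error is √1.137 = 1.07 SD, whatever ρ is.

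**Error using the mean of the two adjacent own scans.** The error variance is 1 + (1 + ρ)/2 − 2ρ = 1.5(1 − ρ). At ρ = 0.8 this is 0.30, an RMS error of 0.55 SD.

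**Error using the group median plus own deviation.** The fill is the others' median at the missed time plus the participant's mean deviation from the others' median at the two adjacent scans. Its error is that of the own-scan mean plus sampling noise from three group medians. At ρ = 0.8 the simulated RMS error is 0.61; 0.61² = 0.37, so the medians add about 0.07 to the 0.30.

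RMS error in between-person SDs, group curve straight across the gap:

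| ρ | Planned group median | Mean of own adjacent scans | Group median + own deviation |
|---|---|---|---|
| 0.3 | 1.07 | 1.02 | 1.10 |
| 0.5 | 1.07 | 0.87 | 0.94 |
| 0.7 | 1.07 | 0.67 | 0.74 |
| 0.8 | 1.07 | 0.55 | 0.61 |
| 0.9 | 1.07 | 0.39 | 0.45 |

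If correlation instead decays with distance between scans (AR(1), where ρ is the correlation between neighbouring scans), the last column becomes 0.86, 0.66, 0.54 and 0.39 at 0.5, 0.7, 0.8 and 0.9.

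**A person far from the middle.** If the true value is 1.5 SD above the group, the planned fill is on average about 1.5 SD too low. Own scans are expected to lie 1.5ρ above the group, so a fill based on them is too low by 1.5 − 1.5ρ: 0.75 SD at ρ = 0.5, 0.45 at 0.7 and 0.15 at 0.9.

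**When the group curve bends.** Plain linear interpolation carries the bend b (the group's departure from a straight line at the missed scan) as bias, so its RMS error is √(1.5(1 − ρ) + b²). At ρ = 0.7 and b = 1 SD this is √(0.45 + 1) = 1.20, worse than the planned 1.07. Group median plus own deviation stays at 0.74, because the group median at the missed time already contains the bend.

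**Carry-through to an analysis.** For illustration, take scans at 0, 0.5, 1, 2, 3, 4, 5 and 6 hours and the area under the curve, a summary the plan does not name. The 3-hour scan carries 1 of 6 hours, or one sixth of the time-averaged area. At ρ = 0.8 the error in that person's average is 1.07/6 = 0.18 SD under the planned rule and 0.61/6 = 0.10 SD under the alternative. With one or three participants each missing one scan, and a true area–symptom correlation of 0.5 (mean sample value about 0.48 with complete data), the planned rule lowers the correlation by about 0.003 at most.

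**The case against.** The strongest reply is that little follows for the results, and most of that stands. A reader might infer that the rule materially weakens the symptom–MRI associations or distorts the group comparisons. The documents do not support this. They give no missingness rate, and with a few isolated gaps the loss is about 0.003 or less in a correlation near 0.48. If groups are compared time point by time point, a false step in one person's curve does not enter the test at all; only the value at that time does.

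A reader might also infer that per-person summaries such as area, peak or change from fasted are damaged. The plan names none of these and does not say how serial values are reduced to one per person, so the effect on its final tests cannot be calculated.

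A further objection is that the obvious remedy, a straight line between the two neighbouring scans, can be worse than the present rule. This also stands: volumes may bend after a meal, and nothing in the documents shows that small bowel water or colonic volume follows a straight course. It counts against linear interpolation, not against using the person's own level.

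Finally, the benefit depends on a within-person correlation that the documents do not give. That is true, and at about 0.3 or less there is none. The study is also a small pilot, and the outcomes affected are secondary. These points limit the importance of the concern but do not justify ignoring relevant data already collected.

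**Conclusion.** The point holds as a minor, inexpensive improvement. The rule covers a single missed scan and makes no use of the participant's own neighbouring scans. The filled value has an RMS error of about 1.07 between-person SDs. Adding the participant's own level gives 0.94 to 0.45 SD over correlations of 0.5 to 0.9, a reduction of 12% (1 − 0.94/1.07) to 58% (1 − 0.45/1.07).

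This rests on 12 per group, equal between-person SD at each scan and equal correlation between scans, none of which the documents state. The equal-SD assumption is least secure for a gap next to the meal, where one neighbour is the fasted scan. The gain is in the accuracy of the affected participant's value and curve. It is not a threat to the study's conclusions unless gaps are much more frequent than assumed here.

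**What to change.** Split the missing-data rule in the Statistical analysis plan. For a missed scan with the participant's own scans on both sides, impute gastric volume, small bowel water and colonic volume as:

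*group median at the missed time + mean of the participant's deviations from the group median at the two adjacent scans*

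Take all three medians over the other participants in the same group. Do not use plain linear interpolation for any of the three outcomes. State separately which rule applies after withdrawal and to gaps at the first or last scan, where there are not own scans on both sides.

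The cost is a few sentences and slightly more calculation, with no new data. The downside is that if the within-person correlation is about 0.3 or less there is no gain, and the fill is slightly worse than the present one (1.10 against 1.07 SD at 0.3).
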